If subjects need to be CCI [REDACTED] for intravenous antibiotics, they should be visited by the research staff for an assessment within 72 hours of admission (where possible). If the subject is CCI [REDACTED] that is not the investigational site, the assessments should be carried out (where possible) by the CCI [REDACTED] under the direction of the investigational site. These assessments will include those collected during exacerbation visits/contacts and will include details regarding any interruption of IMP administration. In these circumstances, every effort should be made to complete all assessments although it is recognised that this might not be possible.

Telephone calls will be made to patients on a weekly basis during a NCFB pulmonary exacerbation until resolution to assess the progression of symptoms and to determine whether systemic antibiotic treatment is ongoing. A telephone script will be provided to sites and responses to standardised questions will be collected in relevant eCRFs.

Resolution of a NCFB pulmonary exacerbation is defined as the date of completion of the required course of systemic antibiotic treatment or the Investigator's judgement that the NCFB pulmonary exacerbation has resolved, whichever is later. This is also the end date of the corresponding AE. Exacerbations occurring less than 14 days after the end of a course of systemic antibiotics for a NCFB pulmonary exacerbation will be considered as a single event (see [Section 10.1.5](#)).

IMP administration may be temporarily interrupted during the time of systemic antibiotic treatment due to a pulmonary exacerbation based on the Investigator's judgement; thereafter, the study treatment should restart as soon as possible. Stop date and re-start date will be recorded in the relevant eCRF. The occurrence of a pulmonary exacerbation does not mandate the discontinuation of the subject from the trial and/or study treatment, unless it occurs between Visit 1 and Visit 2 and/or the Investigator believes discontinuation is in the subject's best interest.

The following assessments will be performed at an Exacerbation Visit or Phone contact, and all details of the pulmonary exacerbation have to be recorded:

- start date and duration of all symptoms since the start;
- all symptoms present which support the NCFB pulmonary exacerbation diagnosis;
- all concomitant medications, especially systemic antibiotics;
- physical examinations and vital signs (if attending the clinic);

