Resolution of a pulmonary exacerbation (and corresponding AE) is defined as the date of completion of the required course(s) of systemic antibiotic treatment and/or the Investigator's judgement that the NCFB pulmonary exacerbation has resolved, whichever is the later of the two dates. The exacerbation end date will be reported at the next scheduled visit or by phone.

A new pulmonary exacerbation is only considered to occur if there are at least 14 days between the end of the course of systemic antibiotics and the onset of new qualifying symptoms. If the subject is not better at the end of an initial 14-day course of systemic antibiotics, then the antibiotic should be continued for an additional standard treatment period or escalated to intravenous therapy in accordance with standard clinical practice.

The treatment of pulmonary exacerbations will follow current treatment regimens used at the respective participating investigational site.

Procedures to be followed in case a subject experiences symptoms suggestive of a pulmonary exacerbation are described in [Section 9.7](#) (Exacerbation Visit/Contact).

CCI

In this trial, CCI

The CCI is a validated 50-item symptom questionnaire developed to measure health status and CCI in subjects with obstructive airway diseases [17, 18]. CCI

Scores will be collected for these 3 domains and the Total score will be produced.

The CCI is a validated, self-administered, patient reported outcome measure assessing CCI and was developed for use in clinical trials and routine clinical practice.

The questionnaires will be completed by the subjects at Visit 2 (Randomisation), and at each subsequent study visit prior to any study procedures using an eCOA device, i.e. SITEpro Tablet. The device will be provided by CCI Inc. and is an electronic data collection system used to collect data at sites.

During Visit 2, appropriate training will be provided to the subjects on how to correctly complete the questionnaires on the device.

To utilise the device, the Investigator has to enter the screening number. Then the device will present the questionnaires for completion by the subject. To ensure that all visits are completed as defined in this CTP, the Investigator will select the appropriate visit number from the options on the screen before handing the device to the subject.

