A supportive analysis will be conducted using an alternative definition of NCFB pulmonary exacerbation. The re-classification of exacerbations will be done in a blinded fashion (before database lock). Alternative definition of pulmonary exacerbation: deterioration in three or more of the following key symptoms for at least 48 hours:

- Cough;
- Sputum volume and/or consistency;
- Sputum purulence;
- Breathlessness and/or exercise tolerance (dyspnoea);
- Fatigue and/or malaise;
- Haemoptysis;

And a physician determines a change in bronchiectasis treatment is required when other potential causes of clinical deterioration have been discounted.

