4.7.4 Method of Analysis for Primary Endpoint

The NCFB pulmonary exacerbations collected from the Pulmonary Exacerbation eCRF form will be considered for the analysis. All cases in which the variable “Do these symptoms meet the protocol-defined criteria for NCFB pulmonary exacerbation?” is not consistent with data collected in the corresponding eCRF Pulmonary Exacerbations Symptoms form will be

CONFIDENTIAL

Sponsor:	Zambon S.p.A.	Protocol Number:	Z7224L02
----------	---------------	------------------	----------

discussed during the blind review meeting. The decisions taken will be documented in the Blind Data Review and Analysis Sets Report.

The start of a protocol-defined NCFB pulmonary exacerbation will be taken as the first day that at least 3 of the 8 defining symptoms occurred concurrently for at least 24 hours as determined by the Investigator, as documented by the start date of the corresponding AE in the eCRF Adverse Events form and reviewed, where necessary, by the DAC (see Section 4.2.1) taking into consideration aspects such as start/stop date and associated systemic antibiotic therapy/hospitalisations.

Only NCFB pulmonary exacerbations with start date \geq date of first IMP dose and \leq date of treatment completion/discontinuation will be considered in the analysis. NCFB pulmonary exacerbations with start date = date of first IMP dose will be discussed on a case-by-case basis during the blind review of the data in order to evaluate whether they should be classified as having occurred in the screening period. The decisions taken will be documented in the Blind Data Review and Analysis Sets Report.

Resolution of a NCFB pulmonary exacerbation is defined as the date of completion of the required course(s) of antibiotic treatment, as collected in the eCRF Systemic Antibiotic Therapy form, and/or the Investigator's judgement that the NCFB pulmonary exacerbation has resolved, as documented by the end date provided for the corresponding AE in the eCRF Adverse Events form, whichever is the later of the two dates. If more than one systemic antibiotic therapy is administered for a NCFB pulmonary exacerbation, then the latest end date will be considered as the date of completion of the required course of antibiotic treatment.

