- a worst case approach will be considered for duration of symptoms and requirement of hospitalisation. For example, if one of two exacerbations considered as a single episode has/have increased dyspnoea for ≥ 24 hours and < 48 hours and the other one has increased dyspnoea for ≥ 48 hours, the single episode will be considered in the analysis as having dyspnoea for ≥ 48 hours.

In order to investigate whether the use of inhaled colistimethate sodium reduces the frequency of pulmonary exacerbations compared to placebo in subjects with NCFB chronically infected with *P. aeruginosa*, the following hypothesis will be tested:

- Null hypothesis: there is no difference between inhaled colistimethate sodium and placebo as regards the effect on the pulmonary exacerbation rate
- Alternative hypothesis: inhaled colistimethate sodium reduces the pulmonary exacerbation rate in favour of inhaled colistimethate sodium compared to placebo.

The null hypothesis must be rejected for the efficacy of inhaled colistimethate sodium to be considered demonstrated.

The number and the percentage of subjects with NCFB pulmonary exacerbations, the number of NCFB pulmonary exacerbations and the total follow-up time in years, as defined in Section 4.1.7, will be summarised by treatment group.

The number of NCFB pulmonary exacerbations during the treatment period will be analysed using a negative binomial model including treatment, country, as detailed in Section 4.9.1, and use of stable concomitant therapy with oral macrolides as fixed effects and log-exposure time on treatment as an offset. The log-time on treatment in years will be calculated as $\ln(\text{exposure time})$.

The adjusted mean annual NCFB pulmonary exacerbation rates in each treatment group and the adjusted rate ratio with their 95% CIs will be estimated by the model. OBSMARGINS option will be used for the estimates. The number of subjects considered in the model will be provided by treatment group.

The number and the percentage of subjects with 0, 1, 2 or >2 pulmonary exacerbations will be presented.

The number and the percentage of subjects with pulmonary exacerbations, the number of pulmonary exacerbations will also be presented by treatment group for severe (defined as those requiring intravenous antibiotics and/or hospitalisation) and not severe exacerbations.

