A simple summary of the annualised pulmonary exacerbation rate will be calculated across subjects for each treatment as $\{\sum_i^{n_j} \text{exacerbation}_i / \sum_i^{n_j} \text{exposure}_i\}$ where j denotes randomised treatment group, $i = 1 \dots n_j$ denotes the number of subjects, exacerbation_i and exposure_i denote the number of exacerbations and exposure time for subject i .

The total duration of systemic antibiotic therapy, overall and by route, will be summarised by treatment group using descriptive statistics for continuous variables as well as distribution frequencies for the following categorisations:

- 1-7 days;

CONFIDENTIAL

Sponsor:	Zambon S.p.A.	Protocol Number:	Z7224L02
----------	---------------	------------------	----------

- 8-15 days;
- 16-30 days;
- >30 days;
- Not Evaluable.

The total duration of systemic antibiotic therapy will be summarised overall and by category.

The duration of systemic antibiotic therapy will be evaluated considering the start and end date of the therapy associated with the pulmonary exacerbation. The duration of each course of systemic antibiotic therapy will be calculated using the following formula:

- Duration (days) = stop date – start date +1

For exacerbations treated with more than one systemic treatment, the duration will be calculated by summing the duration of the associated treatments. The overlapping days will be counted only once.

It is expected that all systemic antibiotic therapy will have completed (i.e. will have a stop date) at the end of the study when data are final, as all therapy stop dates are required to be known in order to derive the resolution date of pulmonary exacerbations per the definition described earlier in this section.

In order to calculate the duration of each course of systemic antibiotic therapy, the following rules will be applied for partial dates of start and stop date of systemic antibiotic therapies:

For the start date:

- if only the day is missing, the first day of the month will be assumed. If the resulting derived date is prior to the start date of the exacerbation, then start date of therapy will be assumed to be equal to the start date of the pulmonary exacerbation.
- if the day and the month are missing, then the date will not be imputed and the duration will be classified as “Not Evaluable”.

For the stop date:

- if only the day is missing, the last day of the month will be assumed;

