- if the day and the month are missing, then the date will not be imputed and the duration will be classified as “Not Evaluable”.

Resultant dates will be discussed during the blind review meeting and documented in the Blind Data Review and Analysis Sets Report.

The above summary/analysis will be performed using the mITT Population and, where appropriate, the PP Population. Results for the PP Population will be considered as supportive.

4.7.4.1 **CCI** Analysis Using Alternative Definition of NCFB Pulmonary Exacerbation

A **CCI** analysis will be conducted using an alternative definition of NCFB pulmonary exacerbation for the mITT Population. The re-classification of pulmonary exacerbations will

CONFIDENTIAL

Sponsor:	Zambon S.p.A.	Protocol Number:	Z7224L02
----------	---------------	------------------	----------

be done during the blind review meeting and documented in the Blind Data Review and Analysis Set Report.

In this CCI analysis, a NCFB pulmonary exacerbation is defined as deterioration in three or more of the following key symptoms for at least 48 hours:

- [REDACTED]
- [REDACTED]
- [REDACTED]
- [REDACTED]
- [REDACTED]
- [REDACTED]

And:

CCI [REDACTED]
[REDACTED]
[REDACTED]

Subjects experiencing NCFB pulmonary exacerbations according to this alternative definition will be identified as those subjects having:

- An AE on the eCRF Adverse Events form with a MedDRA coded Preferred Term of “infective exacerbation of bronchiectasis” that is at least 48 hours in duration (i.e. stop date of AE – start date of AE + 1 ≥ 2);
- At least 3 of the above symptoms on the eCRF Pulmonary Exacerbation Symptoms form for the Pulmonary Exacerbation Number corresponding to that AE, where those symptoms all occur between the start and stop dates of the AE;
- At least 1 therapy on the eCRF Systemic Antibiotic Therapy form for the Pulmonary Exacerbation Number corresponding to that AE.

Analysis will be conducted following the same rules and methods as detailed above for the main definition of NCFB pulmonary exacerbations.

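### The 48-hour test in the alternative exacerbation definition passes any adverse event that touches two dates and never tests symptom duration

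*SAP*

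**What the plan says.** SAP 2.1 gives the alternative definition as "deterioration in three or more of the following key symptoms for at least 48 hours", together with a physician's decision to change treatment. SAP 4.7.4.1 repeats the 48-hour symptom criterion and then lists three conditions that identify qualifying events in the data:

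- an AE coded to the bronchiectasis-exacerbation Preferred Term, with the duration clause "that is at least 48 hours in duration (i.e. stop date of AE – start date of AE + 1 ≥ 2";
- three or more of the listed symptoms on the linked symptom form, all falling within the AE's start and stop dates;
- at least one linked systemic antibiotic.

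SAP 4.7.4.1 assigns the re-classification to the blind review meeting and says the analysis otherwise follows the methods of the main definition. The results go to Table 14.2.1.1.3 (mITT).

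Two other parts of the plan bear on this:

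- **When the AE ends.** Protocol 10.1.5: "Resolution of a pulmonary exacerbation (and corresponding AE) is defined as the date of completion of the required course(s) of systemic antibiotic treatment", or judged resolution if that is later. Protocol 9.7 says of this resolution date: "This is also the end date of the corresponding AE". SAP 4.7.4 treats judged resolution "as documented by the end date provided for the corresponding AE in the eCRF Adverse Events form".
- **How long symptoms last.** Protocol 9.7 has sites record "start date and duration of all symptoms since the start". When SAP 4.7.4 merges episodes it keeps symptom durations apart at 48 hours, in its example of one event with "increased dyspnoea for ≥ 24 hours and < 48 hours and the other one has increased dyspnoea for ≥ 48 hours".

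**The concern.** The definition and the algorithm do not match, for two reasons. First, the formula counts calendar dates touched, not hours elapsed, so a value of 2 does not mean 48 hours. Second, it is applied to the AE, while the definition attaches the 48 hours to the symptoms. The symptom condition asks only that the symptoms fall within the AE dates and sets no minimum duration.

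The analysis is meant to show whether the primary result survives a different exacerbation definition, and the longer duration is one of the main differences from the 24-hour primary definition. If the duration condition does not bind, agreement between the two analyses could be reported as robustness to a 48-hour criterion that was never applied.

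**Working it through.** **Inputs.** The criterion is 48 hours, attached to symptoms (SAP 2.1 and 4.7.4.1). The programmed rule is AE stop date − AE start date + 1 ≥ 2 (SAP 4.7.4.1).

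**The plan's own equivalence.** The rule gives 48 hours only if every date touched is counted as a full day: 2 dates × 24 h = 48 h. That is the inclusive count SAP 4.7.4 uses for antibiotic courses, "Duration (days) = stop date – start date +1". It suits treatment days. The SAP does not state that it applies to a criterion in elapsed hours, and SAP 4.7.6.1 drops the +1 for a time-to-event endpoint because it overstates the time by a day.

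**Elapsed time.** Let d = stop date − start date. The rule d + 1 ≥ 2 is d ≥ 1. With clock times to the minute:

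| d | Passes rule | Shortest | Longest |
|---|---|---|---|
| 0 | no | 0 h | 23 h 59 min |
| 1 | yes | 1 min (23:59 to 00:00) | 47 h 59 min (00:00 to 23:59 next day) |
| 2 | yes | 24 h 1 min | 71 h 59 min |
| 3 | yes | 48 h 1 min | 95 h 59 min |

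- The rule excludes only d = 0, so every event lasting 24 hours or more passes.
- Every AE with d = 1 passes, and none reaches 48 hours.
- From dates alone, d ≥ 2 is necessary for 48 hours and d ≥ 3 is sufficient.

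As an illustration, assume start and stop clock times are uniform over the day. The chance that an AE lasts at least 48 hours is then 0.00 for d = 1, 0.50 for d = 2 and 1.00 for d = 3.

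**AE or symptoms.** Under the Protocol the AE ends at the later of antibiotic completion and judged resolution; under SAP 4.7.4 the AE end date records judged resolution. On either reading it is not the end of the symptom deterioration. Because the third condition requires an antibiotic, most qualifying AEs will probably span well over two dates whatever the symptoms did. Raising the threshold from 2 to 3 or 4 might therefore reclassify few events and would still not test the symptoms.

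**Below 24 hours.** Protocol 9.7 has exacerbations entered in the eCRF whether or not they meet the protocol definition, and none of the three conditions asks for the protocol-defined flag. Unless the sentence carrying over the main rules is meant to import that flag, an event with symptoms lasting under 24 hours could also qualify.

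**The case against.** The strongest reply is that the formula matters little in practice. Protocol 10.1.5 refers to an initial 14-day antibiotic course, so an AE that follows the resolution rule will seldom stop on its second date, and the 1-minute case is an artefact of clock times. That is fair as far as the threshold goes. It also means that the written duration check screens out almost nothing, which makes the missing symptom test the more serious part.

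A second reply is that the intention is visible elsewhere. SAP 4.7.4 separates symptom durations at 48 hours, a cut-point the primary definition does not need; the main rules are carried over; and re-classification takes place at a blind review. This makes a drafting mismatch plausible. But nothing gives the blind review meeting a 48-hour symptom check, the blinded committee in SAP 4.2.1 considers protocol-defined criteria only, and importing the protocol-defined flag would secure 24 hours, not 48.

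A third reply is that the hours may be meant at episode level. Explanatory note 3 in Protocol 10.1.5 reads the 24-hour primary criterion that way and lets individual symptoms be shorter. This is arguable, and the choice belongs to the sponsor. The formula does not deliver 48 hours for the episode either.

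Finally, this is one supportive table. That limits how much weight the point carries but does not remove it.

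**Conclusion.** The concern holds. As written, SAP 4.7.4.1 tests the Preferred Term, the six-symptom list and the antibiotic condition, but not the 48-hour duration in its own definition. The date bounds are exact: the rule removes only same-date AEs, and every AE at its boundary lasts under 48 hours.

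The effect on event counts and on the rate ratio cannot be calculated, because the documents do not give the share of otherwise qualifying events with fewer than three symptoms lasting 48 hours or more. The point is confined to Table 14.2.1.1.3; the primary analysis and the testing hierarchy are unaffected. It should be corrected before that table is used as evidence of robustness to a 48-hour definition.

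**What to change.** Amend SAP 4.7.4.1 before unblinding. After that, SAP section 1 requires the change to be documented, justified and marked as post hoc.

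1. **AE condition:** delete the 48-hour clause and its formula; keep the AE form and the Preferred Term.
2. **Symptom condition:** keep the linkage and timing requirements, and add that at least three of the listed symptoms must each have a recorded duration of 48 hours or more, using the category in SAP 4.7.4.
3. **Antibiotic condition:** leave unchanged.
4. **Missing symptom duration:** name the SAP 4.7.4 rule, which is bounded by the symptom dates and the resolution date of the exacerbation. SAP 4.11 says only that the longest duration is imputed, which could put every missing value at 48 hours or more. The 4.7.4 rule can also exceed 48 hours, because it may run to the resolution date, so report by treatment group how many events qualify only through imputation.

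If the sponsor confirms that an episode-level reading is intended, replace item 2 with a single episode rule based on symptom dates, not AE or antibiotic dates. State whether it uses stop − start ≥ 2 (necessary for 48 hours) or ≥ 3 (sufficient).

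The cost is two bullets of text and one changed derivation, with possibly fewer events in this table. The eCRF form is not in the documents, but Protocol 9.7 has symptom durations recorded, so no new data appear to be needed.

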10.1.5. EFFICACY EVALUATIONS

Protocol-defined Pulmonary Exacerbations

The primary efficacy assessment for an individual subject is the frequency of pulmonary exacerbations.

A pulmonary exacerbation is defined as the presence concurrently of at least 3 of the following 8 symptoms/signs for at least 24 hours:

- increased cough;
- increased sputum volume and/or consistency;
- increased sputum purulence;
- new or increased haemoptysis;
- increased wheezing;
- increased dyspnoea;
- increased fatigue/malaise;
- episodes of fever (temperature $\geq 38^{\circ}\text{C}$ or $\geq 100.4^{\circ}\text{F}$).

And:

it is clinically determined that the subject requires and is prescribed systemic antibiotic therapy. Any occurrence of these symptoms with the prescription of systemic antibiotic therapy, irrespective of cause, should be reported as a pulmonary exacerbation.

For clarification purposes (and the generation of relevant data queries to sites), a further clarification to the protocol definition for pulmonary exacerbations has been provided as follows:

- the presence of 3 or more pre-defined symptoms / signs¹ within any 24-hour period²
- and**
- the episode of exacerbation lasted for at least 24 hours³
- and**
- in the opinion of the Investigator, the subject required and started treatment with systemic antibiotics

Explanatory notes:

¹The pre-defined symptoms / signs are: increased cough; increased sputum volume and / or consistency; increase sputum purulence; new or increased haemoptysis; increased wheezing; increased dyspnoea; increased fatigue / malaise; episodes of fever ($\geq 38^{\circ}\text{C}$ or $\geq 100.4^{\circ}\text{F}$).

²The pre-defined symptoms / signs need to occur within the same 24-hour period (and this defines the start date of the Protocol-Defined Exacerbation) but do not need to be present at exactly the same time.

³The overall episode of exacerbation needs to last at least 24 hours, but individual symptoms / signs can last less than 24 hours (for example, a temperature).

The start date of a **CCI** will be taken as the first day that at least 3 of the pre-defined 8 symptoms/signs occurred concurrently for at least 24 hours, as determined by the Investigator.

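### The SAP 4.7.4.1 algorithm does not implement the alternative exacerbation definition of SAP 2.1: it can drop qualifying events and admit non-qualifying ones

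*SAP*

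**What the plan says.** SAP 2.1 gives the alternative definition as "deterioration in three or more of the following key symptoms for at least 48 hours", followed by a list of six symptoms. It adds the condition that "a physician determines a change in bronchiectasis treatment is required when other potential causes of clinical deterioration have been discounted". It mentions neither AE dates nor coded terms.

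SAP 4.7.4.1 then says how such events will be identified. Three conditions apply:

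- an AE "with a MedDRA coded Preferred Term of “infective exacerbation of bronchiectasis” that is at least 48 hours in duration", with duration tested as AE stop date − AE start date + 1 ≥ 2;
- at least three of the key symptoms on the linked symptom form, "where those symptoms all occur between the start and stop dates of the AE";
- at least one linked systemic antibiotic.

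The AE start date is fixed elsewhere. Under SAP 4.7.4 the start of a protocol-defined exacerbation "will be taken as the first day that at least 3 of the 8 defining symptoms occurred concurrently for at least 24 hours", as documented by the start date of the linked AE. The AE ends at the later of antibiotic completion and the investigator's judgement of resolution (SAP 2.1; Protocol 9.7).

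The primary count is taken from the Pulmonary Exacerbation form (SAP 4.7.4). Protocol 10.1.5 says that qualifying symptoms treated with systemic antibiotics, "irrespective of cause, should be reported as a pulmonary exacerbation". Re-classification to the alternative definition is to be done blinded, before lock, at the blind review meeting, and documented.

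**The concern.** The supportive analysis exists to show whether the primary result survives a different exacerbation definition. That requires the event set to change because the definition changed. Here it also changes with how symptom dates were entered, how the AE was worded and coded, and how long the AE (rather than the symptoms) lasted. If the supportive estimate differs from the primary one, part of the difference may come from the algorithm. If it agrees, the stricter 48-hour requirement may hardly have been applied. The window condition is also open enough that two programmers could build different event sets from the same data.

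**Working it through.** The plan gives no figure to reproduce. The check sets each condition against the definition and tests it on constructed dates.

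**1. Symptom window.** The AE starts when the third symptom is present, so any symptom that began earlier has a start date before the AE. Take three key symptoms of 7 days each (days o to o+6), with the AE starting on the day the third appears and lasting 14 days. These dates are illustrative. All four patterns meet the symptom part of SAP 2.1.

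| Onset days | AE days | Symptoms dated wholly inside the AE | Symptoms present at some time in the AE |
|---|---|---|---|
| 1, 1, 1 | 1–14 | 3 (kept) | 3 (kept) |
| 1, 2, 2 | 2–15 | 2 (dropped) | 3 (kept) |
| 1, 1, 2 | 2–15 | 1 (dropped) | 3 (kept) |
| 1, 2, 3 | 3–16 | 1 (dropped) | 3 (kept) |

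On a start-and-stop-date reading, an event with exactly three key symptoms survives only if all three began on the same day. On a presence reading nothing is lost. SAP 4.7.4.1 does not say which applies. Loss at the end of the window is unlikely, because the AE runs at least to the end of antibiotics.

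**2. Preferred Term.** SAP 2.1 has no coded-term condition. A record on the Pulmonary Exacerbation form, linked to an AE that codes to any other term, fails the first condition whatever its symptoms. No coding convention is given, so the number of such records is unknown.

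**3. The 48 hours.** Turning the date formula into elapsed time:

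| Stop − start + 1 | Elapsed hours possible | Passes ≥ 2? |
|---|---|---|
| 1 | 0 to 24 | no |
| 2 | 0 to 48 | yes |
| 3 | 24 to 72 | yes |
| 4 | 48 to 96 | yes |

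Two calendar dates pass although they span less than 48 hours in all but the limiting case. A value of at least 4 is needed before 48 hours is assured.

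The larger mismatch is that the test is on the AE. Suppose three key symptoms last 30 hours on days 1 and 2, and the AE runs from day 1 to day 14 because of an antibiotic course (illustrative). The formula gives 14 − 1 + 1 = 14, which passes, and all three symptoms lie inside the AE. The event counts, yet no symptom reached 48 hours. Such events are possible: the explanatory notes in Protocol 10.1.5 let individual symptoms of a protocol-defined exacerbation last less than 24 hours.

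**4. A further difference, not relied on here.** SAP 2.1 asks for a change in bronchiectasis treatment; the algorithm requires a systemic antibiotic.

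**The case against.** The best defence is that the SAP uses the same verb for presence: in SAP 4.7.4 symptoms "occur" concurrently for a period, which cannot mean onset. Read that way, the window costs nothing. This stands as far as it goes, and it is why the loss is conditional. But the condition refers to start and stop dates, symptoms carry their own start and stop dates, and no rule settles the reading. The presence reading also does not by itself require three key symptoms to be present together. That gap is narrow for protocol-defined events: at least three of the eight are concurrent at AE start, so it opens only where wheeze or fever, the two signs outside the six, made up part of the trio.

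A reader might infer that a large, known share of events is lost. The documents do not support this. Assume the strict reading, onsets spread evenly over 2 to 4 days, and a 30/40/30% mix of events with three, four and five symptoms: 38–52% would fail. With a 10/20/70% mix the same calculation gives 15–22%, because events with five or more symptoms always keep three. On the presence reading the figure is 0%. Neither the symptom mix nor the onset spread is in the documents.

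A reader might also infer that the Preferred Term wrongly removes pneumonia and COVID-19 events. It may not: the irrespective-of-cause rule belongs to the primary definition, and leaving these events out can fit the alternative definition's clause on other causes. Loss of true exacerbations coded to another term is possible but not shown.

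Finally, re-classification is blinded, reviewed and documented. That guards against bias in the decisions. However, the only criteria supplied to the meeting are the three conditions above, and none of them restores a dropped event or removes a short one.

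**Conclusion.** The algorithm and the definition do not match, and the mismatch runs both ways. Qualifying events can be excluded by the date window (if programmed on symptom dates) and by the single Preferred Term. Non-qualifying events can be included because 48 hours is tested on the AE with a two-date formula. It would therefore be wrong to describe the result simply as a reduced set.

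The size of either error cannot be found from the documents. As a guide to precision only, losing 10% of events widens the confidence interval of the log rate ratio by at most a factor of 1/√0.9 = 1.054, about 5%. Loss at an equal rate in both arms gives no expected bias in the rate ratio, and no mechanism for unequal loss is evident. The primary analysis and the testing hierarchy are untouched; the point concerns one supportive mITT analysis. It is worth correcting because the rule as written can produce the wrong event set, and the information needed to correct it is already collected.

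**What to change.** Before lock, rewrite the identification rule in SAP 4.7.4.1:

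- Build the alternative events from the same linked Pulmonary Exacerbation records as the primary count, whatever the AE's Preferred Term.
- Count an event when at least three of the six key symptoms are present together and each lasts at least 48 hours by its own recorded dates or duration, whether or not it began before the AE start date. Drop the AE-duration formula. The example in SAP 4.7.4 for merged episodes already separates symptoms lasting 24 to under 48 hours from those lasting 48 hours or more.
- State whether the SAP 4.7.4 rule that imputes the longest duration for a symptom with missing duration also applies here, since it could carry symptoms over the 48-hour line.
- Apply the clause on other causes by flagging linked pneumonia, COVID-19 and other non-bronchiectasis AEs for a documented decision at the planned blinded review, not by a single Preferred Term.

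The same edit could say whether the restriction to systemic antibiotics is deliberate. The cost is SAP wording, programming and a little more work at the blinded review. No new data are needed.
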